### **8.8 Stopping Rules**

Please refer to Section 11.1.

## **9.0 DRUG INFORMATION**

### **9.1 Interleukin-2:**

- Chemical Name: Recombinant human interleukin-2 (rhIL-2)
- Other names for the drug: Proleukin, Aldesleukin
- Description: Interleukin-2 is supplied as a sterile, white to off-white, lyophilized cake in single-use vials intended for intravenous (IV) administration
- Classification - type of agent: Cytokine, Antineoplastic Agent, Miscellaneous; Biological Response Modulator
- Mode of action: Immune-stimulator; Binds to IL-2-receptor and activates proliferation of lymphocytes. Interleukin-2 is a human recombinant interleukin-2 product which promotes proliferation, differentiation, and recruitment of T and B cells, natural killer (NK) cells, and thymocytes; causes cytolytic activity in a subset of lymphocytes and subsequent interactions between the immune system and malignant cells; can stimulate lymphokine-activated killer (LAK) cells and tumor-infiltrating lymphocytes (TIL) cells.
- Side effects: Please see the Interleukin-2 Guidance Document for information regarding side effects. For the most recent safety update, please refer to the current package insert(s).
- Drug Interactions: Please see the Interleukin-2 Guidance Document for information regarding drug interactions.
- Contraindications  
Please see the Interleukin-2 Guidance Document for information regarding contraindications.
- Special Warnings and Precautions for Use

Please see the Interleukin-2 Guidance Document for information regarding special warnings and precautions for use.

- Storage and stability: Refrigerator at 2° to 8°C (36° to 46°F). Avoid exposure to heat and light. Stability after reconstitution—24 hours.
- Preparation and Dispensing:  
Please refer to package insert for preparation of this medication.
- Handling and disposal of IL-2 should be per institutional guidelines for the handling and disposal of cytotoxic agents.
- Administration:  
Route of administration for this study: IV infusion over 15 minutes via a central line

Precautions:

Please see the Interleukin-2 Guidance Document for information regarding precautions. For the most recent safety update, please refer to the current package insert(s).

- Availability: Commercially available from Prometheus. Standard of care.

## **9.2 Nivolumab:**

- Chemical Name: Nivolumab
- Other names for the drug: Opdivo, BMS-936558, MDX-1106, ONO-4538
- Description: Nivolumab is supplied a sterile solution (Opdivo Intravenous) which comes in bottles of 40 mg/4 mL (4 mL) or 100 mg/10 mL (10 mL).
- Classification - type of agent: Immunomodulatory; checkpoint inhibitor
- Mode of action: Nivolumab is a fully human IgG4 programmed death 1 (PD-1) immune checkpoint inhibitor antibody that selectively blocks the interaction between PD-1, which is expressed on activated T cells, and PD-1 ligand 1 (PD-L1) and 2 (PD-L2), which are expressed on immune cells and tumor cells.
- Side effects: Please see the package insert(s) for nivolumab. For the most recent safety update, please refer to the current package insert(s).

Treatment-Related Adverse Events Reported in 10% or more of treated patients in either group in the randomized phase 3 trial of nivolumab versus everolimus.

Event	Nivolumab Group (N = 406)		Everolimus Group (N = 397)	
	Any Grade	Grade 3 or 4	Any Grade	Grade 3 or 4
	number of patients (percent)			
All events	319 (79)	76 (19)	349 (88)	145 (37)
Fatigue	134 (33)	10 (2)	134 (34)	11 (3)
Nausea	57 (14)	1 (<1)	66 (17)	3 (1)
Pruritus	57 (14)	0	39 (10)	0
Diarrhea	50 (12)	5 (1)	84 (21)	5 (1)
Decreased appetite	48 (12)	2 (<1)	82 (21)	4 (1)
Rash	41 (10)	2 (<1)	79 (20)	3 (1)
Cough	36 (9)	0	77 (19)	0
Anemia	32 (8)	7 (2)	94 (24)	31 (8)
Dyspnea	30 (7)	3 (1)	51 (13)	2 (1)
Peripheral edema	17 (4)	0	56 (14)	2 (1)
Pneumonitis	16 (4)	6 (1)	58 (15)	11 (3)
Mucosal inflammation	11 (3)	0	75 (19)	12 (3)
Dysgeusia	11 (3)	0	51 (13)	0
Hyperglycemia	9 (2)	5 (1)	46 (12)	15 (4)
Stomatitis	8 (2)	0	117 (29)	17 (4)
Hypertriglyceridemia	5 (1)	0	64 (16)	20 (5)
Epistaxis	3 (1)	0	41 (10)	0

**Ref:** Motzer RJ et al. N Engl J Med 2015;373:1803-1813

- Drug Interactions Please see the Investigator’s brochure and package insert for Nivolumab for information regarding drug interactions.
- Contraindications: Please see the Investigator’s brochure and package insert for Nivolumab for information regarding contraindications.
- Special Warnings and Precautions for Use: Please see the package insert(s) for nivolumab for information regarding special warnings and precautions for use.
- Storage and Stability: Nivolumab vials must be stored at a temperature of 2°C to 8°C and should be protected from light. If stored in a glass front refrigerator, vials should be stored in the carton.

For details on prepared drug storage and use time of Nivolumab under room temperature/light and refrigeration, please refer to the Investigator Brochure section for “Recommended Storage and Use Conditions” and/or pharmacy reference sheets. Briefly, Withdraw the required volume and transfer into an IV container. Dilute with either NS or D5W to a final concentration of 1 to 10 mg/mL. Mix by gentle inversion; do not shake.

Care must be taken to assure sterility of the prepared solution as the product does not contain any anti-microbial preservative or bacteriostatic agent. No incompatibilities between Nivolumab and polyvinyl chloride (PVC), non-PVC/non-DEHP (di(2-ethylhexyl)phthalate) IV components, or glass bottles have been observed.

- Administration: Nivolumab is to be administered as a 60 ( $\pm$  10 minute) intravenous infusion, using a volumetric pump with a 0.2 to 1.2 micron in-line filter at the protocol-specified dose. It is not to be administered as an IV push or bolus injection. At the end of the infusion, flush the line with a sufficient quantity of 0.9% Sodium Chloride Injection or 5% Dextrose Injection.
- Handling and disposal of nivolumab should be per institutional guidelines for the handling and disposal of biologic and cytotoxic agents. Recommended safety measures for preparation and handling of Nivolumab include laboratory coats and gloves.
- Availability: Commercially available from Bristol Myers Squibb (BMS). Standard of care in metastatic renal cell carcinoma.

## 10.0 CORRELATIVES/SPECIAL STUDIES

The planned laboratory correlative studies are to profile the circulating T-cell subsets before and during therapy with IL2 and nivolumab.

We will also archive patient tumor and serum samples for future unspecified testing including but not limited to PD-L1 and anti-drug antibody testing. Submission of samples for correlative studies is expected of all subjects.

### 10.1 Sample Collection Guidelines

An archived tissue block must be identified (to submit unstained slides from) prior to registration. Unstained slides from an archived formalin-fixed paraffin embedded tissue block are to be submitted for each subject from prior nephrectomy or biopsy of metastatic lesion (estimated tumor content >30% of nucleated cells in specimen). This tissue will be archived for future testing, including but not limited to PD-L1 expression and anti-drug antibody testing.

Whole blood samples (20 mL at each time point) will be collected at the time points listed in Section 6.4 Time and Events Table.

Serum samples (5-10 mL) will be collected at the time points listed in Section 6.4 Time and Events Table.

**ALL samples should be labeled with the subject's de-identified study number and collection date. Samples should be overnighted via a courier service and delivered for analysis to:**

**Lab of [name] PhD  
[name] Research Professor of Surgery and Professor of Surgery  
University of Michigan**

Phone [REDACTED]

Email: [REDACTED]

\*\*\*Specimen receiving times are limited to Monday to Friday 8am to 4pm. Specimens should not be shipped on a Friday or the day before a national holiday without prior permission\*\*\*

## 10.2 Assay Methodology

Whole blood Flow Cytometry:

PBMCs will be isolated from the whole blood sample by standard centrifugation. We will analyze the changes of different immune cell sub-population components before and during the course of treatment by FACS with flow cytometry analyzer. These include APC (Antigen Processing Cells) subsets, ILC and NK subsets and T cell subsets.

The staining parameters are as follows:

Staining 1	APC subsets
Staining 2	ILC/NK subsets
Staining 3	T cells subsets - surface
Staining 4	T cells subsets - intracellular

Staining 1	CD45, CD11c, CD14, CD33, HLA-DR
Staining 2	CD45, CD3, CD123, CD127, NKp46, NKp44, CD56, CD161, CD94
Staining 3	CD3, CD4, CD8, CD45RO, CD45RA, PD-1, CD57, CD127, CXCR5, CXCR3
Staining 4	CD3, CD4, CD8, CD57, KLRG1, Tim3, Foxp3, Ki67
Staining 5	CD45, CD3, CD8, IFN $\gamma$ , IL-17, GranB, TNFb, IL-2, IL-22, GM-CSF

## 10.3 Immunogenicity Analysis

Immunogenicity assessment (ADA sampling [including ADA neutralizing antibodies] to identify ADA responses in patient circulation):

Time-points:

Samples for ADA (Anti-drug antibody) analysis will be collected at the time points listed in Section 6.4 Time and Events Table.

Analysis:

Immunogenicity results will be analyzed descriptively by summarizing the number and percentage of patients who develop detectable ADAs against nivolumab.

The immunogenicity titer and presence of neutralizing ADAs will be reported for samples confirmed positive for the presence of ADAs. The effect of immunogenicity on efficacy, and safety will be evaluated, if the data allow.

Method:

The presence of ADAs will be assessed in serum samples taken according to the assessment schedules. At each time point, 20 mL of blood will be drawn for nivolumab ADAs and nivolumab neutralizing antibodies.

Samples will be measured for the presence of ADAs and ADA-neutralizing antibodies for nivolumab using validated electrochemiluminescent (ECL) immunoassays. Tiered

analysis will be performed to include screening, confirmatory, and titer assay components, and positive-negative cut points previously statistically determined from drug naïve validation samples will be used.

ADA samples, if not exhausted by analyses outlined herein, may be retained for 15 years from the patient's last visit date for research purposes.

ADA samples may be disposed of or destroyed and anonymized by pooling after planned analyses.

Incurred sample reproducibility analysis, if any, will be performed alongside the bioanalysis of the test samples. The results from the evaluation will not be reported in the CSR but will be reported separately in a Bioanalytical Validation Report.

#### 10.4 Specimen Banking

Patient samples (tissue, blood, serum) collected for this study will be retained at the University of Michigan. De-identified specimens will be stored indefinitely or until they are used up. If consent for future use of specimens is withdrawn by the subject, best efforts will be made to stop any additional studies and to destroy the specimens.

Specimens being stored long-term for potential use not outlined in the protocol are subject to University Policy Governing Tissue Sample Collection, Ownership, Usage, and Disposition within all UMMS Research Repositories [<http://msa.med.umich.edu/policies/tissue-sample-collection-ownership-usage-disposition-within-all-umms-research-biorepositories>]

#### 11.0 STATISTICAL CONSIDERATIONS

This is a single arm phase Ib/II trial of Nivolumab and IL-2 in patients with Renal Cell Carcinoma. The phase Ib has an endpoint of safety and the phase II primary endpoint is overall response rate (ORR = CR or PR) at 12 weeks. A recently reported trial of Nivolumab after 1 prior therapy in RCC reported had an ORR of 25%. With the addition of IL-2 treatment to nivolumab, we hypothesize an ORR of approximately 46% in this population.

#### 11.1 Study Design/Study Endpoints/Sample Size and Accrual

For the phase 1b portion of the study: We will accrue an initial cohort of 3 patients who will be treated with sequential (rather than interspersed) treatment as follows: they will receive 2 cycles of HD-IL2 given in standard fashion (two 5-day cycles one week apart) followed by nivolumab starting the week after the second IL-2 cycle and continuing every 4 weeks as per standard nivolumab dosing. If 2 or more out of 3 of the first patients suffer a grade 3 or 4 immune related toxicity of interest (see 5.2.1) **within 28 days** from the first dose of nivolumab (**DLT period**) the study will stop. The 4th patient will not be enrolled until after the analysis of the 3 patient cohort is complete and submitted to the regulatory bodies.

If <2 patients suffer a grade 3 or 4 immune related toxicity in the cohort of 3 patients, the study will enroll 7 more patients treated with Nivolumab administered intravenously at 480 mg/dose over 60 minutes every 28 days, starting 1 to 3 weeks after the start date of the first cycle of IL2. We will monitor these patients **continuously** for immune mediated dose limiting toxicities **for 28 days** from the first dose of nivolumab (**DLT period**). Up to 10 total patients will be treated and observed for toxicity for 28 days from the first dose of Nivolumab in the phase 1b portion.

If, at any time during accrual to the phase 1 b portion, 6 patients or more have a grade 3 or 4 immune mediated event of interest (as described in section 5.2.1) we will pause the study and modify/discontinue the protocol in consultation with the site principal investigators and applicable regulatory authorities. If 5 or fewer patients experience grade 3 or 4 immune mediated toxicity of interest (see 5.2.1) during the toxicity window, then the study will continue to the phase II portion.

We choose to examine toxicity after 10 patients because if 6 patients or more are found to have a DLT then the 95% exact binomial confidence interval (26% - 88%) will be > 25% and be indicative that immune mediated toxicity with this regimen is too great.

Dose-Limiting Toxicity is defined as a grade 3 or 4 immune mediated event of interest (as listed and described in section 5.2.1). Please note: immune mediated events of interest do not include those that might occur during high dose IL-2 and are reversible.

DLT evaluable patients: All patients who receive at least 1 dose of HD IL2 and at least 1 dose of Nivolumab will be evaluable for the primary endpoint of toxicity in the phase Ib portion of the trial. Subjects who are not evaluable will be replaced.

The phase II portion of the trial will be a Simon mini-max 2-stage design. The first stage will accrue 12 patients (including any response evaluable patients accrued in the phase 1b portion). If more than 2 patients have a response (CR or PR) out of the 12 patients, then we will accrue 11 more patients for a total sample size of 23 evaluable patients. If more than 8 responses (CR or PR) are observed in the 23 evaluable patients, then we will recommend further study of the combination. This design has 80% power and 10% type I error. If the true ORR of the combined treatment is 25% or less, the probability of early termination of the trial is 39%. If the true ORR is 46% or greater, then the probability of stopping early is only 3.6%. Patients accrued in the Phase Ib portion of the trial will also be included in the Phase II if they are evaluable as defined below.

Response Evaluable Patients: All patients who receive at least 1 dose of Nivolumab and IL-2 will be evaluable for the primary endpoint of overall response proportion in the phase II portion of the trial. If response at 12 weeks is not recorded for the patient, then the patient will be considered a non-responder.

We expect accrual to the entire study to be completed over a period of 24 months.

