#### **Study Endpoints**

##### **Phase Ib portion:**

Primary Endpoint: To establish that the combination of High Dose Interlukin-2 and Nivolumab is safe and tolerable by monitoring 10 patients for immune mediated grade 3/4 events of interest for 28 days from the first dose of Nivolumab.

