## 5.0 TREATMENT PLAN

### 5.1 Treatment Dosage and Administration

Protocol treatment must start within 14 business days of enrollment to the study. The interleukin-2 (Proleukin) and Nivolumab (Opdivo) will be stored and prepared as described in the approved labels.

- 5.1.1 Therapy will start with high dose interleukin-2 (HD IL2) on week1 (day 1-5) and again on week 3 (day 1-5). Nivolumab will start on week 2 (optimally day 1 but can be given up to 3 weeks after IL-2 start but NOT be on the same week as any HD IL2 cycle) and continue every 4 weeks for up to 48 weeks on study unless one of the dose delay or stopping rules apply.
- 5.1.2 HD IL-2 will be administered in standard fashion at a fixed dose of 600,000 IU/kg/dose every 8 hours for a total of up to 14 doses (considered as one cycle) over 5 consecutive days (D1-D5), followed by a 9-day break and then another cycle at the same dose over another 5 consecutive days (D15-D19). Each HD IL-2 course consists of two cycles of up to 14 doses each separated by 9 days of rest.

Monitoring, supportive care measures for HD IL2 will be per institutional guidelines. The standard current guidelines for HD IL-2 administration based on Schwartzenruber et al. have proven to be safe at the participating institutions in the study over the years and will be used for this protocol.

Pre-medications and concurrent medications: Per institutional guidelines at each site usually include anti-emetics, anti-histamines, antipyretics/anti-inflammatory agents, anti-motility/anti-diarrheal agents, proton pump inhibitors, vasopressors as needed, medications for rigors as needed, hydration including boluses and maintenance fluids. It is recommended but not mandated that subjects be given anti-emetics for as needed (prn) use after each IL-2 therapy week to treat residual nausea. Furosemide (a loop diuretic) may also be given per treating investigator's discretion following each IL2 week. Please see IL-2 guidance document for more details.

Subjects will undergo placement of a central venous catheter before each course or cycle of therapy per institutional preferences.

NOTE: If the treating investigator determines another course of HD IL-2 beyond the 2 cycles after week 12 of protocol therapy specified in the protocol are in the

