### Dosing delays:

- **DURING IL-2 weeks**
  - Individual doses of IL-2 within each cycle may be skipped by the treating investigator at his or her discretion. Skipped doses will not be made up.
  
- **AFTER IL-2, BEFORE NIVOLUMAB**
  - All toxicities (with the exception of fatigue) attributed to IL-2 administration should have resolved or recovered to grade 1 or resolved or to baseline prior to starting nivolumab
  - Fatigue should have recovered to grade 2 or better
  - If toxicities have not improved to the levels listed above, nivolumab and the 2nd cycle of IL-2 should be held until toxicities improve to the above levels
  - If nivolumab or IL-2 is delayed >6 weeks as a result of a toxicity, the subject must be permanently discontinued from study therapy with the following exception:
    - If a steroid taper (to manage drug-related adverse events) is the reason for treatment delay of >6 weeks, and the subject's adverse events recover to grade 1 or better, continuation on study could be possible if approved by the principal investigator
  
- **AFTER NIVOLUMAB, PRIOR TO 2nd IL-2 CYCLE**
  - All immune mediated toxicities should have recovered to grade 1 or better prior to starting the second dose of IL-2 and subjects should be off systemic steroids or on a dose of ≤ prednisone 10mg (or equivalent alternative steroid).
  - Fatigue should have recovered to grade 2 or better
  - If specific toxicities are of unclear attribution (including for example: diarrhea, increased LFTs, cardiovascular disorders, mental status changes, pulmonary disorders and rash) they should be treated as possibly related to nivolumab and treated as per the tables in section 5.2.2. These toxicities must improve to grade 1 or better prior to proceeding with the second week of IL-2 therapy.
  - If toxicities have not improved to the levels listed above, nivolumab and the 2nd cycle of IL-2 should be held until toxicities improve to the above levels

- If nivolumab or IL-2 is delayed >6 weeks as a result of a toxicity, the subject must be permanently discontinued from study therapy with the following exception
  - If a steroid taper (to manage drug-related adverse events) is the reason for treatment delay >6 weeks, and the subject's adverse events recover to grade 1 or better, continuation on study could be possible if approved by the principal investigator
  
- **DURING NIVOLUMAB ONLY TIME PERIOD:**

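### The phase Ib DLT window closes 28 days after first nivolumab even when IL-2 cycle 2 is held, so the gate can miss events after IL-2 given on top of nivolumab

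*Combined protocol and SAP*

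**What the plan says.** **Window.** Section 11.1 and the Study Endpoints tie the DLT period to one event, the first nivolumab dose: "Up to 10 total patients will be treated and observed for toxicity for 28 days from the first dose of Nivolumab". The phase Ib endpoint is "To establish that the combination of High Dose Interlukin-2 and Nivolumab is safe and tolerable", judged over those 28 days in 10 patients.

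**Evaluability.** Section 11.1: "All patients who receive at least 1 dose of HD IL2 and at least 1 dose of Nivolumab will be evaluable". IL-2 cycle 1 is enough; cycle 2 is not required.

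**Schedule.** Section 5.1 gives cycle 1 on days 1-5, "followed by a 9-day break and then another cycle at the same dose over another 5 consecutive days (D15-D19". For patients 4-10, "Nivolumab will start on week 2 (optimally day 1 but can be given up to 3 weeks after IL-2 start", but not in an IL-2 week. The first three patients receive both IL-2 cycles first, "followed by nivolumab starting the week after the second IL-2 cycle and continuing every 4 weeks".

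**Holds.** Under Dosing delays in section 5.2, when toxicity after nivolumab has not improved sufficiently, nivolumab and the second "cycle of IL-2 should be held until toxicities improve to the above levels". The outer limit there is: "If nivolumab or IL-2 is delayed >6 weeks as a result of a toxicity, the subject must be permanently discontinued from study therapy", with an exception for steroid tapers. Several tables in section 5.2.1 instead tie resumption of nivolumab and IL-2 to improvement within 12 weeks.

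**Gate.** In section 11.1 the pause rule (6 or more patients) runs while phase Ib accrual is open and states no 28-day limit. The proceed rule (5 or fewer) counts only events inside the toxicity window. The Methodology entry of the synopsis gives the proceed rule without that limit.

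**The concern.** Patients 4-10 are the only phase Ib patients who can receive interspersed treatment, in which IL-2 is given again after nivolumab. The 28-day window observes that re-exposure only if cycle 2 is close to schedule. No section extends the window for a held cycle, requires cycle 2 to fall inside it, or replaces a patient whose cycle 2 was held or dropped.

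A constructed case shows the effect. Nivolumab is given on day 8. A grade 2 immune event, which is not a DLT, occurs on day 13. Cycle 2 is held 28 days and given on days 43-47. Grade 3 immune-mediated colitis follows on day 52. That is 44 days after nivolumab, so the proceed rule scores this patient DLT-free.

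Holds are triggered by toxicity, so the lost observation is not random. The gate also carries weight: section 8.8 refers all stopping rules to section 11.1, section 11.1 has no toxicity rule for phase II, and under section 12.0 the monitoring committee goes from monthly to quarterly meetings once phase II starts.

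**Working it through.** **1. The plan's own figure.** For 6 DLTs in 10 patients, the Clopper-Pearson 95% interval is 26.2% to 87.8%. This agrees with the 26%-88% in section 11.1. The gate's stated arithmetic is right; the question is what enters the count.

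**2. Day arithmetic** (nivolumab on day 8, cycle 2 delayed by d days)

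- Window end: 8 + 28 = day 36.
- Cycle 2 runs from day 15 + d to day 19 + d.
- On schedule (d = 0), observation after cycle 2: 36 - 19 = 17 days.
- Part of cycle 2 outside: 19 + d > 36, so d of 18 or more.
- All of cycle 2 outside: 15 + d > 36, so d of 22 or more.
- Six-week limit: cycle 2 may start on day 15 + 42 = 57, which is 21 days after the window closes.
- Each day that nivolumab starts after day 8 but before cycle 2 adds one day to both thresholds.
- Nivolumab on about day 22: the window runs to day 50, but cycle 2 ended on day 19 if on schedule. Like the three sequential patients, such a patient has no planned IL-2 after nivolumab in the window, even without a hold.

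**3. Are delays this long foreseeable?** Section 5.2 requires immune toxicity at grade 1 or better, and steroids stopped or at no more than 10 mg prednisone equivalent, before cycle 2. The section 5.2.1 tables call for tapers of at least one month for grade 2 pneumonitis and for grade 2 diarrhea or colitis that persists and is treated with steroids. A patient may reach 10 mg before the taper ends, but section 5.2 itself provides for taper delays beyond 6 weeks. These grade 2 events are not DLTs.

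**4. Illustration of size.** The documents give neither DLT rates nor the frequency of holds. Assumptions: DLT rate 25% in the three sequential patients; rate p in patients 4-10 when cycle 2 is inside the window; rate r × p in k delayed patients.

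The lead-in passes with 0 or 1 DLT: 0.75³ + 3 × 0.25 × 0.75² = 0.422 + 0.422 = 0.844. Given a pass, 0 and 1 DLT are equally likely. With X the DLT count in patients 4-10,

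P(6 or more of 10 | pass) = 0.5 × P(X ≥ 6) + 0.5 × P(X ≥ 5),

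where X is the sum of Bin(7 - k, p) and Bin(k, r × p). For p = 0.6:

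- k = 0: 0.5 × 0.1586 + 0.5 × 0.4199 = 0.289.
- k = 3, r = 0.5: 0.5 × 0.0373 + 0.5 × 0.1691 = 0.103.
- k = 3, r = 0.8: 0.5 × 0.0991 + 0.5 × 0.3120 = 0.206.

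| p | r | k = 0 | k = 1 | k = 2 | k = 3 |
|---|---|---|---|---|---|
| 0.4 | 0.5 | 6% | 4% | 3% | 2% |
| 0.6 | 0.5 | 29% | 21% | 15% | 10% |
| 0.6 | 0.8 | 29% | 26% | 23% | 21% |
| 0.6 | 1 | 29% | 29% | 29% | 29% |
| 0.7 | 0.5 | 49% | 38% | 28% | 19% |
| 0.7 | 0.75 | 49% | 43% | 38% | 33% |

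The last p = 0.6 row is the case in which re-exposure adds no risk.

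**The case against.** A reader might infer that the gate does undercount, or that the DLT proportion will understate the regimen's toxicity. The documents do not support that. It would need both long holds and a higher DLT rate after IL-2 re-exposure, and neither is given. The halving in the illustration is a choice, and patients held for early toxicity may well have a higher underlying rate than the others.

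Nor does the text leave the combination unobserved: every evaluable patient has had IL-2 before nivolumab. What can be missed is IL-2 given after it.

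Further points limit the concern:

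- A hold caused by a grade 3-4 immune event of interest inside the window is already a DLT. The gap covers only holds for lower-grade or other non-DLT toxicity.
- The pause rule has no express 28-day limit, so a late event can count while phase Ib accrual is open. This gives no assured protection for the last patients enrolled, and the proceed rule remains window-limited.
- Section 11.1 excludes reversible events that might occur during high-dose IL-2, so some cycle 2 events might not count even inside the window.
- Adverse events are collected to 60 days after last treatment, phase Ib has biweekly cross-site calls, and section 11.2 already summarizes IL-2 cycles and doses. Late events would be known; they would not necessarily enter the gate.
- Even with no delays, p = 0.6 gives only a 29% chance of reaching 6 DLTs. The threshold itself limits the gate more than the window does.

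A fixed window from first nivolumab is a legitimate design choice, and 17 days is a by-product of the day-8 schedule rather than a stated observation need. Both points stand. They bear on how strongly the point is put, not on whether the gap exists.

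**Conclusion.** The point holds as a gap in the rule: a phase Ib patient given nivolumab before cycle 2 can be evaluable and DLT-free before any IL-2 has been given on top of nivolumab. With a day-8 start, delays of 18 days (part of cycle 2) and 22 days (all of it) are the thresholds, and section 5.2 permits longer ones. These thresholds need no assumption beyond the schedule.

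The effect on the gate cannot be sized from the documents. Under the stated assumptions at p = 0.6 with three delayed patients, the chance of reaching 6 DLTs falls by 8 to 19 percentage points (29% to 21% or 10%); it does not change if re-exposure adds no risk. The supportable statement is that the gate can miss such events. The change is worth making because it is cheap and this is the main formal toxicity check before phase II.

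**What to change.** In section 11.1, the Study Endpoints and both synopsis descriptions:

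1. For patients given nivolumab before cycle 2, end the DLT period at the later of 28 days from first nivolumab and 17 days after the last cycle 2 IL-2 dose. Keep 28 days if cycle 2 is permanently omitted.
2. Use this one period in both the pause and the proceed rule, which now differ.
3. Report the DLT proportion also among those of the 10 patients who received IL-2 after nivolumab within their window. Patients without cycle 2, week-4 nivolumab starters and the three sequential patients are then not read as evidence on the interspersed regimen.

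Separately, reconcile the 6-week limit in section 5.2 with the 12-week resumption text in section 5.2.1. No view is taken here on which is right, and no dose or hold rule needs to change for items 1-3.

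**Cost.** Observation time becomes unequal between patients, which the report should state. The gate may also wait longer. At a 6-week delay cycle 2 ends on day 61 and the window on day 61 + 17 = 78, which is 42 days (6 weeks) after day 36 and inside the 12 weeks of weekly contact. On the 12-week text, taken as a 12-week delay of cycle 2, it would end on day 103 + 17 = 120, 12 weeks after day 36. The steroid-taper exception could also take it past 6 weeks.
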